## MAIN STUDY: STEADYRX PROCEDURES

### Overview

The SteadyRx procedures are the primary responsibility of the student investigators in Kalamazoo, who will be overseen by the principal investigator. It is critical that all student investigators are familiar with the SteadyRx Treatment Manual in addition to the policies and procedures specified in this study manual.

### Assessing Videos in SteadyRx

The responsibility of assessing the videos submitted by participants to PillWatch will be the student investigators' in Kalamazoo. Videos will be assessed once per day for all participants by one of the student investigators. The student investigators will create a schedule to equally share this task over the course of the entire study. The student investigators will only use the computers whose IP addresses have been approved by the CTPayer system.

The student investigators will then login using the admin account used to create SteadyRx participants' Motiv8 accounts. Then the student investigators will navigate to the videos tab. All videos marked as unattended should be attended to and then either approved or rejected according to the criteria in the PillWatch training module.

Two of the student investigators will assess each video independently. They will be assigned to be the first or the second appraiser. A schedule has been created in order to split this responsibility evenly. The first appraiser will input their decision in the first appraiser's google sheet in the study google drive. They will then notify the second appraiser that they have done so. The second appraiser will then input their decision in the second appraiser's google sheet. This will automatically update the first appraiser's google sheet. The second appraiser will then open the first appraiser's google sheet to check for agreement. If there is agreement, the second appraiser will log in to the Motiv8 systems website and either accept or reject the video submission. If there is not agreement, the second appraiser contacts the first appraiser to deliberate whether or not to accept or reject the video. If they are unable to reach agreement, they ask the third student investigator to independently review the video submission. The team will either accept or reject the video according to the third student investigator's decision.

The first week that the participant is in the study will be considered a training week. During this time, video submissions will be reviewed by the student investigators, who will provide feedback to the participant to insure that they are submitting videos that meet all of the criteria specified in the PillWatch protocol.

Once all videos have either been approved or rejected, the client's account will automatically update with the \$2 credit for one day of full medication

adherence. Full medication adherence for the day is defined as one accepted video for the OnePerDay group in the allotted dose time window or two accepted videos for the TwoPerDay group in the allotted dose time windows.

A \$6 bonus credit should be given for full medication adherence three days in a row. At the end of every 30-day study period, each participant that has at least 29 days of full medication adherence should be credited \$20. The first two times that a participant has an undetectable viral load at their appointment with their primary care physician at CCP, they will receive an incentive bonus of \$100. All bonus credits should be manually entered into the client's account information via the client's tab in Motiv8. This includes the intake and monthly assessment payments. The student investigators will specify the reason in addition to the amount in order for the client to have a full record.

Only when the participant is due more than \$10 will the student investigators credit their CTPayer card.

## **SteadyRx Video Submission Feedback**

All participants in the SteadyRx group will obtain feedback on their video submissions. The level and detail of feedback is determined by how close the video submissions are to meeting all criteria for acceptance.

**Week One Training.** Participants will be instructed that the first week of participation is a training week, during which videos may be accepted that do not meet all criteria. Participants will receive feedback the day after their first submission, and every other day after the first submission until the end of training week. Feedback will be given by a student investigator calling the smartphone given to them for the study. Student investigators are to identify specific inadequacies in the submissions (e.g., not opening the pill bottle on screen), explain them to the participant, and check for understanding.

**Retraining.** If, after feedback has been delivered twice and there has been no improvement, the student investigator will contact the Outreach Coordinator to schedule an appointment for the participant to come in for retraining. At the appointment, the Outreach Coordinator will go through the training materials and instruct the participant on submitting a video that meets all criteria for acceptance. Participants will be compensated \$20 for returning to Johns Hopkins for retraining.

## **Adverse Events & Study Notes**

**\*\*\* Tracking and reporting adverse events is a \*\*\* critical responsibility of all CLH staff.**

The primary policies and procedures on adverse events and study notes are described below. All staff should review the Study Manual to be sure that they are following the procedures appropriately.

**Tracking & Reporting Adverse Events.** An adverse event is any bad thing that happens to a participant. This could include feeling sick or chronically tired, getting mugged on the streets of Baltimore, or any other bad thing you can imagine, even shark attacks and hang glider accidents.

If any member of the research team learns of an adverse event, it is their responsibility to file an adverse event report and bring the event to the attention of the Outreach coordinator and Principal Investigators.

**Incarceration.** The investigator and outreach coordinators must be immediately notified if a participant becomes jailed or otherwise imprisoned, is enrolled in a halfway house, or enters a constant monitoring procedure managed by any part of a criminal justice system. Under any of these conditions, an Adverse Event Report must be written. The IRB must be notified of any incarcerations at the time of continuing review. In order to avoid a reset, an incarcerated participant must supply a urine sample within two days of release, and then resume a normal testing schedule thereafter. Incarceration will not have any effect on discharge date or any aspect of study procedures except as specified above.

**Study Notes.** **ALL RESEARCH STAFF ARE RESPONSIBLE FOR WRITING STUDY NOTES.** Any adverse events should also be entered into the SteadyRx Study Note System. To access this system, open the SteadyRx folder in the BERC folder on Google Drive and click on the Google Sheet with the filename “Study Notes.” In addition to writing a study note for any and all adverse events, study notes should be written for ANY deviation from the standard protocol of this study, and for ANY important information not entered elsewhere. If any decision had to be made that was not already specified this Study Manual, then a study note should be made.

The basic rule of creating a study note is this: If you think there is any chance that a study note should be created, then a study note should be created. Specific examples of reasons to write a study note include any study-wide or participant-specific changes in contingencies or policies; any unintentional changes in procedure due to computer or staff error; any alteration in pay not specified in the protocol, or accidental payments or underpayments made to any participant. Once you are done writing the study note, notify the principal investigator.

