### Monthly Assessments

**Reminder Calls.** Participants will be given reminder calls related to their scheduled monthly assessment by the student investigators. They will also receive follow up calls if they fail to show up for their scheduled appointment time. Reminder calls will be given one day before their scheduled appointment. The calls will be between 10AM – 6PM Monday through Thursday and 1PM – 5PM on Sunday.

If the participant does not answer, the student investigator will wait one hour and then call again. This process is repeated if they do not answer again. If they do not answer a third time, the student investigator will leave the following voicemail:

*“Hi (PERSON’s NAME), my name is \*First Name\* and I am calling on behalf of the SteadyRx research team. I just wanted to remind you that you have your monthly assessment scheduled for (APPOINTMENT TIME) tomorrow and confirm that you will be coming. Thank you and have a nice day.”*

If someone other than the participant answers the phone, follow the following script:

*“Hi, I’d like to speak to (PERSON’S NAME).” If the person on the phone asks who you are or why you are calling then say, “My name is \*First Name\* and I am calling to remind them about an appointment they have at Johns Hopkins tomorrow.” If they ask for further details tell them “I’m sorry, but I am only allowed to discuss details with (PERSON’S NAME).”*

Once the participant is one the phone, follow the following script:

*“Hi (PERSON’S NAME), my name is \*First Name\* and I am calling on behalf of the SteadyRx research team. I just wanted to remind you that you have a monthly assessment scheduled for (APPOINTMENT TIME) tomorrow and confirm that you will be coming.” If they say yes, say “Okay, great, remember that your appointment is at (APPOINTMENT TIME) and that you need to*

*bring your pill bottle and will be paid \$30 for completing the interview and you will receive an additional \$20 for bringing your pill bottle. That means you will be paid up to \$50 tomorrow for bringing your pill bottle and completing the interview."Once they respond, then say "Okay, see you at (APPOINTMENT TIME) tomorrow, have a great day, Bye."*

If they indicate that they are unsure, or do not know what you are talking about, follow the following script:

*"[name] asked me to call you because you are scheduled to come in for your monthly assessment interview tomorrow for the SteadyRx research study you are participating in."*

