Reminder calls will be discontinued immediately upon request of the participant, will not exceed three per week, and will be discontinued after one month from the originally scheduled intake interview or appointment time.

**Collection Schedule.** Scheduling monthly assessments is the responsibility of the outreach coordinator and the student investigators in Kalamazoo. Both are responsible for different aspects of the monthly assessment protocol. Monthly assessments should be scheduled to occur every 30 days over the course of 180 days (for a total of six monthly assessments after random assignment). The first monthly assessment is scheduled for 30 days after the day of random assignment. During the Monthly Assessment Interview, the outreach coordinator should review and update the [Monthly Assessment Checklist-Outreach Coordinator](#), and the student investigator should update the [Monthly Assessment Checklist-WMU staff](#). The outreach coordinator should keep a record of all scheduled assessments, which should include their PTID, the scheduled date for all assessments, whether or not the assessment was collected for all planned assessments to date, the date that each collected assessment was actually conducted, the number of days that passed between the planned collection date and the actual collection date, and summary data indicating the overall percentage of planned assessments that have been collected to date and the average days from planned collection to actual collection for all collected assessments to date.

**Contacting No-Shows.** The student investigators are responsible for contacting participants who do not show up for monthly assessments. Any participant who does not show up for a monthly assessment at their scheduled time should be contacted via phone by student investigators reminded of their appointment, reminded of the \$50 they can earn, and rescheduled if necessary. Participants can also be contacted by using the information on the participant contact information sheet that was completed as part of the intake or most recent monthly assessment. Any updates that occur to the contact information should be noted on the most recent contact sheet. If necessary and if time allows, then the outreach coordinator can travel to the participant's residence to conduct the monthly assessment. A

record of all attempts to call no-shows should be kept on a separate log.

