**Elements of the monthly assessments.** The outreach coordinator will be responsible for:

- Attaching the MEMS reader to the assessment computer
- Obtaining CD4 and HIV-1 RNA levels from medical record
- Scheduling the next monthly assessment

**Reading a participant's MEMS cap.** Upon a participant's arrival, the outreach coordinator will place the MEMS cap on the reader and initiate the reading.

Tutorials for reading a MEMS cap will be made available to the outreach coordinator from the student investigators as well as from the help section located within the database. They will obtain CD4 and HIV-1 RNA levels from the medical record or from printed labs given by the participants. The outreach coordinator will inform WMU staff of the participant's arrival and any new lab information.

**Conducting Monthly Assessments.** The remainder of the monthly assessment will take place over the phone with one of the student investigators located in Kalamazoo. The student investigator is responsible for reading each assessment question aloud to the participant and filling in the answers accordingly. Upon the completion of both the MEMS reading and phone assessments, the participant should be paid \$50. If the participant brought in recent CD4 and RNA lab readings and have an undetectable viral load, they should be paid \$100, up to twice during the study. All relevant data logs should be updated (see [Monthly Assessment Checklist – WMU Staff](#)).

The student investigator is solely responsible for conducting the following assessments:

- [Visual Analog Scale for self-reporting ART adherence](#)
- [Medical Outcomes Study HIV Health Survey](#)
- [Addiction Severity Index-Lite](#)
- [Patient Reactions Assessment](#)

In addition to the previous assessments, student investigators are also responsible for conducting the following assessments for participants in the SteadyRx group:

- [SteadyRx Satisfaction Questionnaire](#)
- [Software Usability Measurement Inventory](#)

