Secondary and Exploratory Analyses. Continuous measures assessed repeatedly over time (bottle openings, CD4, HIV-1 RNA, and MOS-HIV) will be analyzed using a longitudinal linear regression model, analogous to that used for the primary outcomes. We will control for baseline values in the CD4, viral load, and MOS-HIV models. Measures assessed only at intake will be analyzed via linear or logistic regression as appropriate. Baseline predictors of response to treatment, including positive urine screen for cocaine or opioids, health literacy (TOFHLA), depression (BDI), psychological factors (SCL-90), job and educational history (VEA), and executive function (Wisconsin Card Sorting) will be assessed by fitting regression models with interactions between treatment assignment and each predictor variable, to determine if the effect of treatment on outcome varies as a function of each of these predictors. Similar models, with an interaction between treatment group and drug use, adherence to buprenorphine/methadone, and attendance to primary care, respectively, (as time-varying covariates) will allow us to determine whether these variables affects response to treatment.

Usage, Acceptability, and Cost. Acceptability and SUMI global scale scores, app uses per day, daily duration of use, and cost of the app and incentives and ICER will be summarized via descriptive statistics (mean, SD, medians, histograms).

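### Adverse events are captured passively while SteadyRx participants have more exposure to staff, so recorded counts may be biased upward in that arm and events may be missed in both

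*Combined protocol and SAP*

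**What the plan says.** **Capture rule.** The Adverse Events & Study Notes section defines the event very broadly: "An adverse event is any bad thing that happens to a participant". Reporting is triggered by knowledge: "If any member of the research team learns of an adverse event, it is their responsibility to file an adverse event report". For incarceration and similar criminal-justice monitoring, "Under any of these conditions, an Adverse Event Report must be written". That rule covers both arms, but it too depends on the team being told.

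**Contact common to both arms.** Under Monthly Assessments, "Monthly assessments should be scheduled to occur every 30 days over the course of 180 days", which gives six assessments, and "Reminder calls will be given one day before their scheduled appointment". The outreach coordinator handles the MEMS reading, the laboratory values and the next appointment. For the interview, "The student investigator is solely responsible for conducting the following assessments": the adherence visual analog scale, MOS-HIV, ASI-Lite and the Patient Reactions Assessment. No adverse event question is listed. The checklists linked from this section are not reproduced.

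**Contact in SteadyRx only.** The monthly interview adds a satisfaction questionnaire and the SUMI. Under SteadyRx Video Submission Feedback, "Participants will receive feedback the day after their first submission, and every other day after the first submission until the end of training week", by telephone, with a retraining visit if repeated feedback brings no improvement. Under Assessing Videos in SteadyRx, submissions are reviewed daily and each is judged by two student investigators.

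**Analysis.** The Analytic plan contains no adverse event analysis. Its between-arm list reads: "Continuous measures assessed repeatedly over time (bottle openings, CD4, HIV-1 RNA, and MOS-HIV) will be analyzed using a longitudinal linear regression model". Self-reported opiate and cocaine days are an exploratory measure under Secondary Outcome Variables, but in the Analytic plan drug use appears only as a predictor or moderator of treatment response.

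**The concern.** With so open a definition and no scheduled question, what is recorded depends on what happens to come up when staff and participants are in touch. Every SteadyRx-only element adds opportunity in that arm and none adds it in control. A by-arm listing of events would then mix true frequency with opportunity to notice.

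This matters for a pilot that pays cash incentives to people with substance use disorder, because tolerability is something its report should be able to describe. A SteadyRx excess could be real or could be detection, and a real excess could be explained away as extra contact. Similar counts would not reassure either if most events in both arms went unasked and unrecorded. With about 25 participants per arm, a handful of differentially noticed events could change the picture. No later analysis can recover events that were never asked about.

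**Working it through.** The documents give no adverse event rate or detection probability, so there is no stated figure to reproduce. Two checks are possible.

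**1. Scheduled live contacts over 180 days, per participant**

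- Both arms: 6 assessments + about 6 reminder calls = 12 (Monthly Assessments).
- SteadyRx adds about 3–4 week-one calls (Video Submission Feedback): 12 + 3 = 15 to 12 + 4 = 16.
- Ratio: 15/12 = 1.25 to 16/12 = 1.33. Without reminder calls: 9/6 = 1.50 to 10/6 = 1.67.
- Not counted: no-show calls (both arms), conditional retraining visits, and feedback after week one, for which no frequency is stated. The two extra questionnaires lengthen existing interviews and add no new contacts.
- Video review: 180 videos (once-daily dosing) or 180 × 2 = 360 (twice-daily) for a fully adherent participant. This is one-way viewing.

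**2. Effect on recorded counts at equal true rates**

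Let *p* be the chance that an event surfaces through contact common to both arms, and *q* the chance that it surfaces through SteadyRx-only contact. Both are assumptions.

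- Control detection = *p*; SteadyRx detection = 1 − (1 − *p*)(1 − *q*).
- Recorded ratio, SteadyRx to control: R = 1 + *q*(1 − *p*)/*p*.
- If extra detection acts only on events in the first 7 of 180 days: R₁ = 1 + (7/180)(R − 1).

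| *p* | R at *q* = 0.1 | R at *q* = 0.5 |
|---|---|---|
| 0.2 | 1.40 | 3.00 |
| 0.3 | 1.23 | 2.17 |
| 0.5 | 1.10 | 1.50 |
| 0.8 | 1.025 | 1.125 |

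Over the same grid, R₁ runs from 1 + (7/180)(0.025) = 1.001 to 1 + (7/180)(2.00) = 1.078. If *q* = 0, both ratios are exactly 1.

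**In counts.** Assume 2 true events per participant and 25 participants per arm, so 50 events per arm, with *p* = *q* = 0.3.

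- Control records 50 × 0.3 = 15 and misses 35.
- SteadyRx records 50 × (1 − 0.7 × 0.7) = 25.5 if the extra detection acts throughout, or 15 × [1 + (7/180)(0.7)] = 15.4 if it acts only in week one.

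**With a common question.** If asking both arms raised *p* to 0.95 (assumed), R would be 1 + 0.1 × 0.05/0.95 = 1.005 to 1 + 0.5 × 0.05/0.95 = 1.026, against 1.23–2.17 at *p* = 0.3.

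**The case against.** The strongest reply has four parts.

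- **The contact gap is modest.** A reader might infer that SteadyRx participants are contacted far more often, so that counts will differ. That holds only if viewing a video counts as contact. Once reminder calls are included, live scheduled contact is about 12 against 15–16, and the extra scheduled calls all fall in week one and concern video quality. This stands. It limits the claim to a possible upward bias of unknown size.
- **Nothing planned is affected.** No between-arm adverse event test exists. This also stands, but any descriptive table by arm would carry the same problem.
- **Health is measured equally in other ways.** A reader might infer that drug-use days are the only harm-relevant measure collected alike in both arms. They are not: MOS-HIV, ASI-Lite, CD4 and HIV-1 RNA are also collected in both, and all but ASI-Lite are named in the between-arm models. This stands, but these measures do not capture discrete events such as injury or incarceration.
- **The checklists may hold an adverse event item.** They are not reproduced, so this cannot be excluded. It limits certainty. If there is such an item, the Monthly Assessments and Adverse Events sections should say so, since neither does now.

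It is also fair to say that the omission of drug-use days from the between-arm models is a separate matter. It lends no weight to the ascertainment point.

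**Conclusion.** The point holds in moderate form. As written, capture is passive, no query is listed among the monthly elements, and exposure to staff is unequal by arm. Any bias from that inequality would run upward in SteadyRx, and under-recording is possible in both arms. The size cannot be fixed from the documents. It may be negligible (1.00–1.08 if the extra detection is confined to week one) or substantial (up to 3.00 at the extreme of the assumed grid, with extra detection throughout follow-up). All of these ratios rest on assumed detection probabilities. The documents do not support saying that counts will differ, or that a planned safety test is compromised. What is affected is the descriptive safety account.

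As a separate and secondary matter, the exploratory outcome of opiate and cocaine days has no named between-arm analysis. The section on data analysis for future publication refers only generically to outcome measures being analyzed by GEE and does not name it.

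**What to change.** 1. Add one identically worded adverse event question, covering the time since the last assessment, to the monthly interview in both arms, and name it in the Monthly Assessments section. If the checklists already contain one, state that instead.
2. Record for each event how it became known.
3. Base any by-arm adverse event table on answers to the common question, and list events learned through SteadyRx-only contact separately.
4. Separately, add self-reported opiate and cocaine days to the between-arm longitudinal models in the Analytic plan.

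**Cost.** Items 1–3 add one question at six existing interviews and one field on the report form. The real burden is more minor events: under the present definition each needs a report, a study note and notification of the coordinator and investigators. Item 4 is one more model on data already collected monthly in both arms.

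The final data-analysis section is written in the past tense. If follow-up is complete, the question can no longer be asked. The report should then say that events were passively collected, give the source of each where the study notes show it, and label any added drug-use model according to when it was specified.
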